9.2 General aspects

Descriptive statistics will be based on means (+/- standard deviation) or medians [minimum-maximum] depending on the distribution of quantitative variables. Qualitative variables will be described in terms of numbers and percentages. Univariate comparisons will use the usual statistical tests after verification of the distribution of the variables (Chi2 or Fisher's test, t-test, anova or their non-parametric equivalents Wilcoxon and Kruskal-Wallis tests).

The tests will be performed at the 5% significance level. The 95% confidence intervals will be provided for each estimate.

Measures of association between quantitative variables will be made using Pearson's or Spearman's correlation coefficients depending on the distribution of the data. Measures of association between qualitative variables will be performed using the Chi-square or Fisher test depending on the distribution of the data.

The agreement between quantitative variables will be evaluated using the Bland-Altman method and that between qualitative variables using the Kappa coefficient.

Calculations will be made using IBM SPSS v21 and R software (version 3.6.1, www.R-project.org).

9.3 Potential variables of the ultrasound score

Structures assessed		Results	Weighting
Language			
	Abnormal movement	Yes/No	
	> 1 attempt identified	Yes/No	
	Range of motion	< threshold > threshold (only to be defined)	
	Thickness	< threshold > threshold (threshold to be defined)	
Suprahyoid muscles			
	Signal strength (Heckmatt score)	1-4	
	Poorly defined fat involution and muscle boundaries	Yes/No	
	Decreased surface area compared to contralateral	Surface < threshold (threshold to be defined)	
	Thickening fraction compared to contralateral	< threshold > threshold (only to be defined)	
Geniohyoid			
	Decreased thickening fraction	< threshold > threshold (only to be defined)	
Laryngeal ascension			
	Ascension measured indirectly by assessment of hyoid bone ascension	< threshold > threshold (only to be defined)	

9.4 Determination of classes and thresholds of quantitative variables

The hypothesis of a linear relationship between the logit of the diagnosis of swallowing disorders objectified by VFSS and the quantitative variable will be tested. If it is verified, the variable will be dichotomised. The threshold used will be determined using ROC (Receiver

Operating Characteristic) curve analysis, which will allow the threshold for which sensitivity and specificity are maximum to be retained. (62)

The variables for which the hypothesis is not verified will be split into classes. (63)

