1.3.3 Ultrasound evaluation

It allows the qualitative and quantitative assessment of the structures involved in the three phases of swallowing: the strength of the tongue, the kinetics of the lingual propulsion, the thickness of the supra- and infra-hyoid muscles at rest and during swallowing, the ascent of the hyoid bone and the larynx, and the mobility and diameter of the upper esophageal sphincter.

The application of ultrasound in swallowing assessment has been described for many years. (33) It is an easy to use, reproducible, bedside tool that is non-invasive and non-irradiating.

Ultrasound assesses the kinetics of the tongue for abnormal movements and the contractility and thickness of the oropharyngeal muscles to diagnose possible dysfunction. (34)(35)

Ultrasound will allow quantitative and qualitative analysis of lingual kinetics during swallowing, in particular looking for abnormal movement patterns. (36)(37)

It is also possible to quantify the movement in search of a propulsion defect. (38)(39) It also allows qualitative and quantitative assessment of the geniohyoid, mylohyoid and digastric muscles.

The thickness of these muscles at rest and during swallowing and their echogenicity can be quantified.(40)(41) The measurement of the thickness of these muscles is reproducible and its accuracy in assessing the digastric muscles has been compared with MRI, showing a very good correlation. (42)(45)

During this second phase of swallowing, it will also be possible to measure the duration and distance of hyoid bone elevation, reflecting laryngeal elevation. (43)(44)(45) A decrease in hyoid bone elevation associated with a decrease in lingual contraction capacity as seen on ultrasound can explain dysphagia. (46)

Finally, ultrasound can be used to assess the displacement and diameter of opening and closing of the upper oesophageal sphincter (USO), allowing the detection of dysphagia related to USO damage. (47)

This ultrasound evaluation will complement the clinical evaluation of reflexes, cranial pairs or the patient's posture or vigilance, with a quantitative analysis of the structures mentioned above, for which the clinical examination lacks precision and reliability and needs to be supplemented by complementary examinations. (48)(49)

This quantitative, reproducible, non-invasive, non-radiating, bedside ultrasound analysis represents a promising tool for clinical practice to monitor patient progress. (50)

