9.5 Selection of variables to be included in the score

Patients will be classified into 2 groups according to the diagnosis obtained with VFSS: positive group (presence of swallowing disorders) and negative group (absence of swallowing disorders). The ultrasound variables will be compared between the 2 groups by appropriate tests according to the type of variables (quantitative or qualitative) and their distribution. The results of these comparisons will be used to select the ultrasound variables showing a difference between the 2 groups ($p < 0.20$) for inclusion in the multivariate logistic regression. (62)(63)

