9.6 Weighting of variables

The previously selected ultrasound variables will be included in the model predicting the presence of swallowing disorders. Multiple logistic regression with variable selection using the Akaike information criterion (AIC) method will be used. The presence of multicollinearity between variables will also be investigated and the variable eliminated if necessary.

Variables that do not improve the predictive model will thus be removed from the score.

The scores for each variable resulting from the multivariate logistic regression will be used to weight each variable in the ultrasound score. (62)(63)

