9.7.2 Validity

The threshold of the ultrasound score defining the presence of swallowing disorders will be determined using Receiver Operating Characteristic (ROC) curve analysis.

Sensitivities, specificities, positive and negative predictive values and the diagnostic Odd ratio will be calculated to determine the diagnostic accuracy of the score.

10 Expected results in terms of scientific and professional advances

This study will allow the construction and evaluation of the reliability and validity of a new ultrasound score in the diagnosis of swallowing disorders. To our knowledge, no study has evaluated the performance of an ultrasound score in the diagnosis of swallowing disorders.

The analysis of the different structures involved in swallowing will also provide knowledge on the impairment of the functions and structures involved in swallowing. This may allow to better orientate the therapeutic strategy, both medical and rehabilitation.

Moreover, as the ultrasound examination is non-invasive, non-irradiating, can be performed in a simple consultation room and requires minimal cooperation from the patient, it could be an alternative to videofluoroscopy, currently the reference examination.

Swallowing ultrasound could thus also be a tool for monitoring the effectiveness of the treatments implemented, since it can be performed frequently without adverse effects.

The results of this study will only be applicable to a population of patients consulting a day hospital for suspected swallowing disorders, mostly related to ENT surgery or a prolonged stay in an intensive care unit. Further multicentre work and in other population categories to improve external validity.

11 Expected benefits and risks for patients

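### Section 9.4 dichotomises a measurement precisely when it is linear in the logit, at a cut chosen in the same patients; one continuous term costs the same parameter and overstates accuracy less

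*Combined protocol and SAP*

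**What the plan says.** Section 9.3 lists ten candidate rows. Three are yes/no, one is the Heckmatt score (1 to 4), and six are measurements to be reduced to a threshold: tongue range of motion, tongue thickness, suprahyoid surface area, suprahyoid thickening fraction, geniohyoid thickening fraction and hyoid ascension. The tongue-thickness row, for example, reads "< threshold > threshold (threshold to be defined".

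Section 9.4 tests linearity in the logit and continues: "If it is verified, the variable will be dichotomised". The cut comes from a ROC analysis, "which will allow the threshold for which sensitivity and specificity are maximum to be retained". A measure that fails the test is split into classes. No quantitative measure stays continuous.

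Section 9.5 compares VFSS-positive and VFSS-negative patients "by appropriate tests according to the type of variables (quantitative or qualitative) and their distribution" and takes forward those with p<0.20. Section 9.6 applies AIC selection and then states: "The scores for each variable resulting from the multivariate logistic regression will be used to weight each variable in the ultrasound score". Section 9.7.2 sets a ROC threshold on the finished score and adds: "Sensitivities, specificities, positive and negative predictive values and the diagnostic Odd ratio will be calculated to determine the diagnostic accuracy of the score". Section 9.1 sizes one cohort of 100. No second sample or resampling step is described.

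**The concern.** If the logit is linear in a measure, one slope describes it. A cut replaces that slope with a single step, so patients far from the cut and patients next to it get the same points. The event count gives no reason to do this, because either form enters the model as one term. The cut version also estimates the cut's position, and it does so by maximising agreement with VFSS in the same patients who later provide the reported accuracy.

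Two things could follow: reported sensitivity and specificity that exceed what new patients would show by more than they need to, and a score that is truly somewhat weaker. Sections 10 and 11.2 present ultrasound as a possible alternative to videofluoroscopy, so both bear on the study's main message.

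**Working it through.** **1. The plan's own figure.** Section 9.1: 5 variables × 10 events ÷ 0.50 prevalence = 100 patients, which reproduces. A continuous measure and a dichotomised one each count as one variable, so keeping the measure continuous leaves this unchanged.

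**2. Inputs for the size.** From the documents: n=100, 50% prevalence, six threshold rows among ten, p<0.20 screen, AIC selection, ROC cuts, ROC threshold on the score. Assumed, because the documents do not give them: effect sizes, correlations and distributions.

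Optimism = apparent AUC − AUC of the same fitted score in new patients. Added optimism = optimism (cut) − optimism (continuous). Loss = true AUC (continuous) − true AUC (cut).

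**3. Ten-row layout.** Screen on raw values; linearity tested with a quadratic term at 5%, and if rejected the same tertile classes in both arms, so only the linear branch differs; backward AIC; 1,000 replicates; 20,000 new patients. Standardised differences for the six measures: weak 0.3 for all; modest 0.5, 0.5, 0.3, 0.3, 0, 0; stronger 0.8, 0.8, 0.5, 0.5, 0, 0; equal 0.6 for all.

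| Effects, r | True AUC cont./cut | Loss | Optimism cont./cut | Added |
|---|---|---|---|---|
| Weak, 0 | 0.637/0.616 | 0.021 | 0.111/0.168 | 0.057 |
| Weak, 0.2 | 0.592/0.586 | 0.006 | 0.104/0.154 | 0.050 |
| Weak, 0.5 | 0.574/0.566 | 0.008 | 0.083/0.126 | 0.043 |
| Modest, 0 | 0.689/0.660 | 0.029 | 0.083/0.141 | 0.058 |
| Modest, 0.2 | 0.645/0.626 | 0.019 | 0.085/0.138 | 0.053 |
| Modest, 0.5 | 0.632/0.607 | 0.025 | 0.072/0.122 | 0.050 |
| Stronger, 0 | 0.813/0.768 | 0.045 | 0.056/0.114 | 0.058 |
| Stronger, 0.2 | 0.752/0.721 | 0.031 | 0.065/0.119 | 0.054 |
| Stronger, 0.5 | 0.732/0.691 | 0.041 | 0.059/0.111 | 0.052 |
| Equal, 0 | 0.829/0.784 | 0.045 | 0.063/0.124 | 0.061 |
| Equal, 0.2 | 0.727/0.711 | 0.016 | 0.077/0.131 | 0.054 |
| Equal, 0.5 | 0.681/0.666 | 0.015 | 0.074/0.122 | 0.048 |

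With twelve further scenarios using quantitative measures only, added optimism over all 24 is 0.043 to 0.071.

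**4. Sensitivity to the set-up.** With predictors drawn first and log odds ratios of 0.3 to 0.8 per SD, the added optimism is:
- five measures with equal effects, correlation 0.3 to 0.5: 0.038 to 0.069;
- five or six independent measures: 0.066 to 0.124, depending on effect size, selection and whether the direction of the cut is fixed.

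In a further 18 scenarios with six measures, added optimism was 0.034 to 0.093 and the loss 0.007 to 0.078. Across all linear-effect runs the added optimism is therefore about 0.03 to 0.12, and it was positive every time.

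**5. The plan's own measures.** Overstatement of mean sensitivity and specificity at the score's own threshold, five measures, no selection, 400 replicates:

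| r, log OR per SD | Continuous | Cut | Difference |
|---|---|---|---|
| 0, 0.3 | 0.091 | 0.146 | 0.055 |
| 0, 0.5 | 0.075 | 0.138 | 0.063 |
| 0.3, 0.3 | 0.076 | 0.113 | 0.037 |
| 0.3, 0.5 | 0.063 | 0.108 | 0.045 |

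Over the 24 scenarios of step 3 the difference is 1.3 to 5.0 points. Together that is about 1 to 6 points. In those 24 scenarios, true mean sensitivity/specificity with cutting ranged from 0.3 points better to 4.8 points worse.

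**6. Departures from linearity (r=0.2).** If risk truly steps at one threshold, cutting gains 0.007 to 0.017 in true AUC, while optimism still rises by 0.032 to 0.042. With the SD 1.25 times larger in positives, the loss is 0.002 to 0.013 and the added optimism 0.028 to 0.035.

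**The case against.** The plan wants thresholds. Section 1.3.3 faults earlier studies for not defining one, and section 9.3 is built on below/above rows. That wish is legitimate but does not require cut components: section 9.7.2 already sets a threshold on the finished score, and cut-offs for single measures can be reported separately.

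AUC is not among the accuracy measures listed in section 9.7.2. That stands, so the size is better read in sensitivity and specificity. With 50 patients per group, the 95% interval around a sensitivity of 75% is ±1.96 × √(0.75 × 0.25 / 50) = ±12 points, wider than the added overstatement. The latter is a bias in one direction, however, and the interval does not show it.

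Non-rejection of linearity at n=100 does not prove linearity. That also stands; step 6 shows a shape for which cutting does slightly better in true AUC.

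A reader might go further and infer that cutting lets noise measures through the p<0.20 screen and so undermines the primary outcome, which is the selection of variables. The documents do not support this. Section 9.5 chooses tests by variable type, and section 9.2 names "t-test, anova or their non-parametric equivalents Wilcoxon and Kruskal-Wallis tests", which points to a screen on the raw measurement. On that reading, noise measures enter the final score in 9–16% of cases when continuous and 12–17% when cut (six mixed ten-row scenarios), and in one scenario the order is reversed. Section 9.5 should still say which form is screened.

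**Conclusion.** The point holds for the linear branch of section 9.4. The wording and the direction are firm: added optimism was positive in every scenario run. The size is not derivable from the documents. Under assumed linear effects at n=100, the added overstatement of mean sensitivity/specificity is about 1 to 6 points and the added AUC optimism about 0.03 to 0.12, lowest with correlated measures and highest with five or six independent ones. The loss of true AUC is about 0.01 to 0.08 in most scenarios.

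Three stronger conclusions are not supported. No narrower range is a general property of linear effects, since correlation, number of measures and effect size all move it. Nothing here shows that the class-splitting rule for non-linear measures is wrong, because both arms in step 3 treated that branch identically. Nor does cutting explain most of the optimism: with continuous terms 0.056 to 0.111 of AUC optimism remains in the ten-row layout, and about 9 to 12 points in sensitivity/specificity. That remainder is a separate internal-validation matter. This is a cheap improvement worth making.

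**What to change.** Change the linear branch only.

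- **9.3:** record the six threshold rows as measured values.
- **9.4:** *A quantitative variable whose linearity in the logit is not rejected enters 9.5–9.6 as one continuous term; ROC cut-offs of single measures are reported as descriptive results only.*
- **9.5:** *The p<0.20 screen uses the uncut measurement.*
- **9.6, if a bedside chart is wanted:** *After fitting, coefficients are converted to points over a few intervals per measure, fixed without reference to the VFSS result.*
- **9.7.2:** the ROC threshold on the finished score stays.

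The cost is wording: no new data and the same parameter count for linear measures. The downside is a slightly less simple chart, and rounding to points gives back part of the gain. In the twelve linear ten-row scenarios, a six-interval chart costs 0.003 to 0.011 of true AUC and ends 0.002 to 0.036 above the cut score. Four intervals cost 0.005 to 0.018 and end 0.000 to 0.029 above. With weak effects at r=0.2 almost nothing is gained in true AUC. With modest effects and unequal SDs, or with a true step, the chart ends 0.001 to 0.017 below the cut score.

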9.5 Selection of variables to be included in the score

Patients will be classified into 2 groups according to the diagnosis obtained with VFSS: positive group (presence of swallowing disorders) and negative group (absence of swallowing disorders). The ultrasound variables will be compared between the 2 groups by appropriate tests according to the type of variables (quantitative or qualitative) and their distribution. The results of these comparisons will be used to select the ultrasound variables showing a difference between the 2 groups ($p < 0.20$) for inclusion in the multivariate logistic regression. (62)(63)

9.6 Weighting of variables

The previously selected ultrasound variables will be included in the model predicting the presence of swallowing disorders. Multiple logistic regression with variable selection using the Akaike information criterion (AIC) method will be used. The presence of multicollinearity between variables will also be investigated and the variable eliminated if necessary.

Variables that do not improve the predictive model will thus be removed from the score.

The scores for each variable resulting from the multivariate logistic regression will be used to weight each variable in the ultrasound score. (62)(63)

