9.1 Calculating the size of the study

The calculation of the number of subjects required is based on the number of explanatory variables to be included in the multiple logistic regression model to construct the ultrasound score. The "1 variable per 10 events" rule is applied. (61)

A total of 5 variables will be collected and analysed as described above (see 9.5), with an estimated prevalence of swallowing disorders of 50%.

There are therefore potentially 5 variables to be included in the predictive model, i.e. a required number of 100 patients.

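### Section 9.6 sets no penalisation or separation rule for the score weights, so a rare sign absent from all VFSS-negative patients could be retained with an infinite weight

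*Combined protocol and SAP*

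**What the plan says.** All references are to the combined protocol and SAP.

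- **Weights (9.6).** Variables that pass the univariate screen of 9.5 (p<0.20) enter a multiple logistic regression with AIC selection. Then: "The scores for each variable resulting from the multivariate logistic regression will be used to weight each variable in the ultrasound score". The text does not say whether these are coefficients, odds ratios or rounded points. The only safeguard on the coefficients is a multicollinearity check.
- **Predictors (9.3, 9.4).** The table in 9.3 has ten candidate rows: three yes/no signs (one is "Poorly defined fat involution and muscle boundaries"), the four-grade Heckmatt score, and six rows to be cut at a threshold. In 9.4, quantitative variables that are linear in the logit are dichotomised at a ROC cut-point. For the rest, "The variables for which the hypothesis is not verified will be split into classes".
- **Sparse tables (9.2).** For univariate comparisons the plan lists "Chi2 or Fisher's test". The weighting step has no equivalent provision.
- **Size (9.1).** The rule is "1 variable per 10 events". The inputs are "A total of 5 variables will be collected and analysed" and "with an estimated prevalence of swallowing disorders of 50" per cent, "i.e. a required number of 100 patients".

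**The concern.** A logistic coefficient for a yes/no item is a log odds ratio. If no VFSS-negative patient shows the sign, the likelihood keeps rising as the coefficient grows, and no finite estimate exists. Software prints a large number that depends on when the iteration stopped. Sections 9.1 to 9.7 say nothing about what to do then.

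The primary outcome in 3.1 is the choice of variables for the score, and the weights are what turn those variables into a score. With a separated item, the Weighting column of 9.3 either cannot be filled for that row or holds an arbitrary number that outweighs every other item. The analyst would have to drop, cap or merge the item after seeing the results. Section 9.7.2 then estimates accuracy, with no separate data set named for it.

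A second, milder matter is that ordinary maximum-likelihood coefficients are biased away from zero, on average, when events per variable are few.

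**Working it through.** **1. The plan's own figure.** N = variables × events per variable / prevalence = 5 × 10 / 0.50 = 100, which reproduces 9.1. This gives 50 VFSS-positive and 50 VFSS-negative patients. With the ten rows of 9.3 as candidates, events per variable are 50/10 = 5.

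**2. Would the planned steps stop a separated item?** Take a sign in a/50 positives and 0/50 negatives. AIC keeps a one-parameter item if its likelihood-ratio statistic exceeds 2. For a=4 the expected counts are 2, 48, 2 and 48, so LR = 2[4 ln(4/2) + 46 ln(46/48) + 50 ln(50/48)] = 5.71. The univariate Firth estimate is ln[(a+0.5)(50.5) / ((50−a+0.5)(0.5))].

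| a | Fisher p | Chi-square p (uncorrected) | LR | ML weight | Firth weight |
|---|---|---|---|---|---|
| 2 | 0.495 | 0.153 | 2.81 | infinite | 1.65 |
| 3 | 0.242 | 0.079 | 4.25 | infinite | 2.01 |
| 4 | 0.117 | 0.041 | 5.71 | infinite | 2.28 |
| 6 | 0.027 | 0.012 | 8.70 | infinite | 2.69 |

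The item passes p<0.20 from a=4 by Fisher, or from a=2 by uncorrected chi-square. Taken alone, AIC keeps it from a=2. These figures are exact for 50/50.

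**3. How often would a zero cell occur?** The documents give no sign frequencies, so the frequency q among VFSS-negatives is an assumption. The chance of none among m negatives is (1−q)^m:

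| q | m=50 | m=39 | m=19 |
|---|---|---|---|
| 2% | 36% | 45% | 68% |
| 5% | 8% | 14% | 38% |
| 10% | 0.5% | 2% | 14% |

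The column m=50 is the plan's case. The other two correspond to the 61% and 81% prevalences that section 1.1 quotes for head and neck cancer and stroke, and are illustrative only.

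The sign must also be common enough in positives to pass the screen. At 50/50 this matters little: with q=2% and the sign in 20% of positives, the chance of 0 negatives and at least 4 positives is still 36%. With 19 negatives it matters a great deal. Fisher p<0.20 then needs at least 11/81 positives, so for a sign in 10% of positives the 68% falls to 12.5%.

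In simulation (n=100, 50% prevalence) with one rare strong sign (frequency 8%, odds ratio 20), 46% of fits after screening and AIC had a non-finite weight. With common signs (frequency 40%) the figure was 0%.

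**4. The other weights.** Two sets of simulations with assumed effects, before any selection:

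- 5 predictors (10 events per variable): a true weight of 1.10 averaged 1.17-1.21, and a true 1.0 averaged 1.09-1.11. That is about 6-11% too large.
- 10 candidates (5 events per variable): 1.27-1.29 against 1.10, and 1.16-1.18 against 1.0. That is about 15-18% too large.
- Firth brought these averages to 1.08-1.12 against 1.10, and 0.99-1.01 against 1.0.
- A single weight exceeded its true value in 53-56% of studies with 5 predictors and 60-61% with 10. All five predictors did so together in only 6-8%.

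**5. With selection kept.** After Fisher p<0.20 and backward AIC, retained weights of true value 1.0 averaged 1.27 (5 candidates) and 1.31 (10) by ordinary regression, against 1.20 and 1.23 by Firth. Most of the excess comes from selection and remains.

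**6. Does inflation matter to the score?** If every weight is multiplied by the same c>0, each patient's score becomes c times itself. Ranking, ROC curve and classification at the rescaled threshold are unchanged. A separated item is different, because only one weight runs away. In simulated separated data sets its median was 25.8 at 25 iterations, while the other four averaged 1.17-1.20.

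**The case against.** The strongest reply is that separation is hypothetical. VFSS-negatives here are not healthy controls: all have an indication for videofluoroscopy (4.1), and most day-hospital patients have sarcopenia, ENT cancer or long ventilation (1.2). Six of the ten rows in 9.3 are cut at a threshold and need not be rare. At 10% in negatives a zero cell is a 1-in-200 event. **This stands**: the problem is conditional on rare, specific signs or sparse classes.

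It can also be said that an analyst would notice a coefficient above 20. That is likely, but the plan gives no rule for what follows.

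The word used in 9.6 is not tied to coefficients, and it cites published point scores. Still, points derived from an infinite coefficient or odds ratio are equally undefined.

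A reader might infer that some sign will get an infinite weight and that all other weights will come out too large. The documents support neither. No sign frequency is given, the inflation holds only on average, and separation itself adds little to the other weights. A reader might also take the listing of Fisher's test in 9.2 as proof that sparse tables were expected. It appears there only among the usual tests.

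**Conclusion.** The point holds in a limited form. As written, 9.6 can produce a weight with no finite value, and the planned screen and AIC would not prevent it. That part is exact. Its probability is not known from the documents: 36%, 8% or 0.5% per sign at an assumed 2%, 5% or 10% in 50 VFSS-negatives, and higher if several sparse items are offered or negatives are fewer.

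The average inflation of the remaining weights is real but secondary. Its size rests on assumed effects and frequencies, and the part common to all weights has no effect on ranking or ROC. Most of the excess after selection is not a matter of which likelihood is used. ROC-chosen cut-points were not part of the simulations in steps 4 and 5 and should add to it.

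This is a worthwhile correction to an unspecified step. It does not show that the score would fail.

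**What to change.** In 9.6, state: the weights will be the coefficients of the selected variables, estimated by Firth's penalised-likelihood logistic regression, with penalised-likelihood confidence intervals. The p<0.20 and AIC steps can stay. The sentence also settles what is meant by the scores from the regression.

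**Cost.** One sentence and a different function in R, which 9.2 already names. Patients, data and N are unaffected. Firth shifts predicted probabilities slightly toward 0.5, which does not affect a score used with a ROC-chosen threshold.

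**What it does not do.** It leaves the inflation from choosing variables and cut-points in the same data. In simulation the median calibration slope moved only from 0.80 to 0.86 with 5 predictors and from 0.60 to 0.69 with 10. The gain in out-of-sample AUC was 0.004 or less. A bootstrap of the whole selection process, or shrinkage, would be a separate addition.
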